Sample size was estimated based on the hypothesis that HBE would produce a difference of at least 10% in RDQ and SF-36 scores. Effect size (Cohen d) was calculated as 0,49 keeping in mind an RDQ mean and standard deviation of 3,3±1,0 previously found in Spanish population with symptomatic GERD²⁴ and an SF-36 mean and standard deviation of 56,9±20,3 reported in Italian population in medical therapy with PPI²⁵. The minimally important difference selection was chosen based on the assumption that any difference smaller than 10% would have no clinical relevance. Based on this data, 14 patients per group would yield a power greater than 80% for detection of a minimally important difference as large as or larger than 0,6 points in RDQ questionnaire (range: 1 to 6) and 10 points in SF-36 questionnaire (range: 0 to 100), when using a paired t test as described in the statistical analyses plan section. Because of a complementary analysis of crossover data is planned with McNemar marginal homogeneity test, effect size was recalculated based on results of a previous trial²⁰, according to which, 58,8 % and 28,6% of placebo-treated patients in pre-omeprazole era, reported improvement of GERD symptoms with and without a HBE of 20 cm, respectively. Based on these data, and maintaining a statistical power of 80%, required sample size was adjusted to a total of 34 patients. In

figure 2, matrices for sample size calculation are shown, based on the cited trial and using internationally accepted statistical procedures²⁶. Likewise, in table 3 an output of sample size calculation is shown from G*Power 3.1.9.2 (Universität Düsseldorf, Düseldorf, Germany) software²⁷. Finally, calculated sample size was increased by 20% in order to avoid study power loss due to drop-outs or losses of follow-up. Thus, final sample size was 42 patients, 21 per group.

T test	Means: Difference between two dependent means	(matched pairs)
Analysis	A priori: Compute required sample size	
Input	Tails	One
	Effect size dz	0,4926108
	A err prob	0,05
	Power (1- β err prob)	0,8
Output	Noncentrality parameter δ	2,5596808
	Critical t	1,7056179
	Degrees of freedom	26
	Total sample size	27
	Actual power	0,8015888
McNemar	Proportions: Inequality, two dependent groups	
Analysis	A priori: Compute required sample size	
Input	Tails	One
	Odds ratio	3,571
	α	0,05
	1- β	0,8
	Prop discordant pairs	0,53782
Output	Lower critical N	13,0000000
	Upper critical N	13,0000000
	Total sample size	34
	Actual power	0,8169370

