Cross-over: After allocation has been completed, patients in the intervention group will receive a pair of numbered wooden prisms with dimensions 20x18x18 cm along with written instructions about the correct use of the intervention. The patient must sleep with HBE during 6 weeks and both RDQ and SF-36 questionnaires will be applied again at the end of this first period while the participant is still sleeping with HBE. Afterwards, a washout 2 week period follows in which the participant sleeping with HBE will stop using it and will return the pair of wooden prisms to the researchers. After washout period has ended and both RDQ and SF-36 questionnaires have been applied again, patients allocated to the control group during the first period of the study will receive a random pair of prisms and will be instructed to use the prisms for sleeping with HBE during a second period of 6 weeks. Meanwhile, participants initially allocated to the HBE group will be followed as a control group in this second period of the study.

Blinding: Because HBE is not susceptible to double-blinding, patients allocated to the intervention group will always be aware of the group they belong to. However, the researcher in charge of statistical analysis of data and writing the results report will work with random-generated alphabetical group codes for masking the intervention in each one of the periods of the trial.

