Follow-up: After participant allocation, telephonic follow up will be made during both periods of the trial with a frequency that is dependent on the intervention group of the patient in that period. Participants in the HBE group will be called weekly for 2 weeks, and then will be called biweekly for a month, until each period of 6 weeks has ended. In contrast, patients in the control group will be called every three weeks along each period. With the purpose of verifying both HBE adherence and correct use of wooden prisms, every participant will be asked to send a photograph of the bed head legs during the follow-up telephone call. The photograph will be received by the researcher via e-mail or smartphone and will be encoded and saved in a hard disk. At the end of the first period, RDQ and SF-36 questionnaires will be applied and researchers will store the returned prisms during washout period. When washout period has ended, RDQ and SF-36 questionnaires will be applied again in order to be sure of the absence of any carry-over effect in the group initially allocated to HBE. Finally at week 14, RDQ, SF-36 and Patient Preference questionnaires will be administered to complete study ending outcome assessments.

In figure 5, a schematic representation of follow-up is shown.

[figure not shown]

Figure 5: Schematic representation of photographic and telephonic follow-up. W1-6: Weeks from 1st to 6th in each period.

Primary outcome:

1. Effectiveness: Change of ≥ 0,6 points between basal RDQ questionnaire and the same questionnaire administered after 6 weeks of HBE use.

Secondary outcomes:

- 1. Quality of life: Change of ≥ 10 percentage points between basal SF-36 questionnaire and the same questionnaire administered after 6 weeks of HBE use.
- **2. Patient preference:** Proportion of patients who preferred HBE, after finishing 14 weeks of the study.
- 3. Safety: Proportion of patients with any reported adverse event during HBE or without bed inclination.

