Statistic analysis plan: Quantitative and qualitative variables collected with Basic Data Format, RDQ, SF-36 and Patient Preference questionnaires will be typed in a Microsoft Excel 2007 database. Intervention groups will be masked with an alphabetical code provided by an independent collaborator who will not be involved with data analysis or report writing. For statistical processing, database will be imported into STATA SE 13.0 for Windows (StataCorp LP, Texas, USA) and descriptive statistics will be generated for each variable. Statistically significant differences will be searched for categorical data using the Chi-square test or Fisher exact test and normality will be tested for numerical continuous variables using the Shapiro-Wilk test. For normally distributed continuous variables, statistically significant differences will be searched for by using unpaired Student's t test. Alternatively, for not normally distributed variables Mann-Whitney U test will be applied. For non-normal variables due to atypical data, values outside the percentile 50 ± 1,5 interquartile range were excluded. For complementary processing of primary outcome and secondary outcome quality of life, score difference

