between periods will be transformed into a binomial variable and a McNemar marginal homogeneity test will be applied. McNemar mid-p was used if discordant pairs sum was smaller than 25²⁸. Differences with one-tail p<0,05 will be accepted as statistically significant. Exploratory subgroup analysis will search for differences stratified according to age group, sex, ethnic group, BMI, comorbidities, cups of coffee per day, pharmacological adherence, and length and severity of symptoms; among other 16 baseline variables. Subgroup interactions will be tested with Chi-square or Fisher exact test, and effect size was expressed as a univariate relative risk from a generalized linear model of binomial family. As part of internal quality control of the clinical trial, a pre-test was applied to prove the assumption of a negligible *carry-over* effect, according to expert guidelines²⁹. Analysis of variance (ANOVA) for crossover studies was used in search for significant sequence, period and treatment effects, assuming a negligible *carry-over* effect. In the modified intention to treat analysis, participants with protocol violations because of bad adherence to HBE, were included, but it was not possible to include patients who withdrew from the study because outcome information could not be gathered completely.

Methodology diagram: A schematic representation of the trial methodology is presented in figure 6.

[figure not shown]

Figure 6: Schematic representation of the trial methodology. RDQ: Reflux Disease Questionnaire; SF-36: Short Form 36 Questionnaire; HBE: Head of Bed Elevation; Standard treatment: Based on proton pump inhibitors and/or sodium alginate, according to treating physician criteria.

WORK TEAM

Work team of this clinical trial is formed by three authors. The respective roles during the design and conduction of the trial, and also the professional profiles of each researcher are described below.

Researchers:

- [name] (Principal Researcher study design, patient recruiting, telephonic follow-up, outcome assessment, statistical analysis, writing of final report)
 - General Practice Physician Universidad Nacional de Colombia
 - 3rd year Internal Medicine resident Universidad Nacional de Colombia
- [name](Researcher patient recruiting, intervention administration, clinical and telephonic follow-up, writing of final report)
 - General Practice Physician Universidad Nacional de Colombia

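### The plan names no paired test for the within-patient adverse-event comparison, so by default it falls to Chi-square or Fisher, which ignore the pairing

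*Combined protocol and SAP*

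**What the plan says.** Under Secondary outcomes, safety is defined as: "Proportion of patients with any reported adverse event during HBE or without bed inclination". Under Cross-over, each control patient later receives the prisms, and "participants initially allocated to the HBE group will be followed as a control group in this second period of the study". A patient who completes the study therefore gives one yes/no result under each condition.

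The Statistic analysis plan has one general rule for categorical variables: "Statistically significant differences will be searched for categorical data using the Chi-square test or Fisher exact test". A paired method for binary data appears once, and the sentence limits it to two outcomes, neither of them safety: "For complementary processing of primary outcome and secondary outcome quality of life, score difference". The mid-p version applies below 25 discordant pairs. The cross-over ANOVA in the same section names no outcome and is not a method for yes/no data.

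The significance rule is "Differences with one-tail p<0,05 will be accepted as statistically significant". The hypotheses under Sample size give a direction for RDQ and SF-36 only. The plan does not assign safety a paired test, restrict it to the first period, or say that it will only be described.

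**The concern.** Chi-square and Fisher on HBE periods against control periods treat N patients as 2N unrelated people. The variance they assume omits the within-patient covariance. A patient who readily reports events, or has events from background medication, may well report in both periods. The covariance is then positive, the assumed variance is too large and the p-value too high. For a harm comparison, the likely error is to report no difference when the paired data show an excess under HBE.

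The plan already accepts that a binary outcome in this design calls for McNemar: it sized the trial that way. Safety was left out of that treatment.

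**Working it through.** **Inputs from the document.** One-tailed 0.05 (Statistic analysis plan); 34 pairs before drop-out and 42 after (Sample size); mid-p below 25 discordant pairs. **Assumed, because not given:** event rates of 40% v 20%, 30% v 10%, and 30% in both periods; within-patient correlation ρ from −0.1 to 0.5.

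**1. The plan's own paired binary calculation.** "Based on these data, and maintaining a statistical power of 80%, required sample size was adjusted to a total of 34 patients". Table 3 gives a discordant proportion of 0.53782 and an odds ratio of 3.571. Discordant pairs: 34 × 0.53782 = 18.29, taken as 18. Probability that a discordant pair favours HBE: 3.571 / 4.571 = 0.781. With X binomial (18), P(X ≥ 13) is 0.8169 at 0.781 and 0.0481 at 0.5. These match Table 3 (critical value 13, power 0.8169370, alpha 0.0481262).

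**2. What ignoring the pairing does to the variance.** For paired proportions,

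Var(difference) = [pA(1−pA) + pB(1−pB) − 2ρ√(pA(1−pA)pB(1−pB))] / N.

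An independent-groups test drops the last term. At 40% v 20% the bracket is 0.24 + 0.16 − 2ρ√(0.24 × 0.16) = 0.400 − 0.392ρ:
- ρ = 0: 0.400, nothing lost.
- ρ = 0.3: 0.282; the unpaired standard error is too large by √(0.400/0.282) = 1.19.
- ρ = 0.5: 0.204; too large by √(0.400/0.204) = 1.40.

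**3. Exact power and error.** All possible paired tables were enumerated from the multinomial distribution with p11 = pA·pB + ρ√(pA(1−pA)pB(1−pB)). Each test was applied at one-sided 0.05, with Chi-square uncorrected.

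| 34 pairs | ρ | Fisher | Chi-square | McNemar mid-p |
|---|---|---|---|---|
| Power, 40% v 20% | 0 | 45.6% | 57.7% | 55.5% |
| | 0.3 | 44.8% | 59.2% | 67.2% |
| | 0.5 | 43.4% | 60.4% | 80.6% |
| Power, 30% v 10% | 0 | 56.0% | 70.3% | 65.1% |
| | 0.3 | 56.7% | 73.6% | 77.6% |
| Error, 30% in both | −0.1 | 3.3% | 6.1% | 4.9% |
| | 0 | 2.7% | 5.2% | 4.8% |
| | 0.5 | 0.4% | 1.2% | 3.7% |

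With 42 pairs, 40% v 20% and ρ = 0.5, power is 57.4%, 69.9% and 88.8%.

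**4. Illustration with 42 pairs (invented counts).** Events in both periods 5, HBE only 7, control only 1, neither 29. The margins are 12/42 and 6/42.
- Chi-square: pooled rate 18/84 = 0.2143; SE = √(0.2143 × 0.7857 × 2/42) = 0.0895; z = 0.1429/0.0895 = 1.595; one-sided p = 0.055.
- Fisher, one-sided: p = 0.091.
- McNemar mid-p on 8 discordant pairs: P(X = 8) + ½P(X = 7) = 1/256 + 4/256 = 5/256 = 0.020.

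Here the default tests miss 0.05 and the paired test meets it. The correlation in these counts is about 0.49, towards the high end of the assumed range.

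**The case against.** Several objections have weight.

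*The plan never assigns Chi-square or Fisher to safety.* The sentence is generic. The section's list of data sources (basic data, RDQ, SF-36 and preference forms) does not mention adverse events, which the Specific Objectives assign to telephone follow-up. No safety hypothesis is stated, and descriptive statistics are promised for every variable. A reader might infer that the plan prescribes a wrong test for its formal check on harm. The text does not go that far: the rule reaches safety only because safety is categorical and nothing else covers it. But an analyst following the text would still have no paired test.

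*The loss rests on an unknown correlation.* A reader might infer that the safety p-values will simply be wrong. At zero correlation Chi-square is close to nominal (5.2%) and slightly more powerful than mid-p. The only joint distribution in the document, Figure 2 for symptom improvement, multiplies the margins (0.588 × 0.714 = 0.420; 0.412 × 0.286 = 0.118), which is zero correlation. That concerns another outcome and is a sizing convention, but the document offers no evidence of positive correlation for adverse events.

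*Chi-square would not always miss an excess.* With 34 pairs, 4 events in both periods, 6 under HBE only and none under control only, one-tailed Chi-square gives 0.036, Fisher 0.066 and mid-p 0.008. A two-sided calculation (Chi-square 0.072) would suggest a miss, but two-sided testing is not the plan's stated rule.

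*Valid uses of these tests exist.* They include a first-period comparison, or sequence against direction of discordance. The plan states neither.

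*A paired test does not cure everything.* During HBE, patients are called weekly for 2 weeks and then biweekly for a month, about 4 calls; controls are called every three weeks, about 2. Reported events may differ for that reason alone. Complete-pair McNemar also omits patients who withdrew, and it ignores period effects.

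**Conclusion.** The point stands in limited form. The safety data are paired, McNemar is named only for two other outcomes, and the remaining rule for categorical data ignores the pairing. The consequence depends on the assumed correlation. With 34 pairs and 40% v 20%, Chi-square falls short of mid-p by 67.2 − 59.2 = 8.0 points at 0.3 and 80.6 − 60.4 = 20.2 points at 0.5, and has no shortfall at zero. Fisher falls short throughout: 9.9, 22.4 and 37.2 points at 0, 0.3 and 0.5. The plan does not say when Fisher would replace Chi-square.

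The documents do not support saying that the trial will miss harm. Safety is a secondary outcome with no stated power. What can be said is that the default discards information the design collects, and the plan already contains the remedy. The undefined tail for safety is part of the same gap.

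**What to change.** In the Statistic analysis plan:
- State that the proportions of patients with any adverse event under HBE and without it will be compared within patient by McNemar, with mid-p below 25 discordant pairs, and reported as a paired risk difference with its 95% confidence interval.
- State whether the safety test is one- or two-sided and, if one-sided, in which direction.
- Restrict Chi-square and Fisher to comparisons between different patients, such as baseline characteristics by sequence.
- Report descriptively the events in patients who withdrew before completing both periods, since complete-pair analysis omits them.
- Note that more frequent calls during HBE may raise reported events, and interpret any excess with that caveat.

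The cost is a few sentences. The method is already planned for other outcomes, and no extra patients are needed. The statistical downside is small: if events are uncorrelated within patient, mid-p has about 2 points less power than Chi-square at 40% v 20% (57.7 − 55.5) and about 5 at 30% v 10% (70.3 − 65.1), with 34 pairs.

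### The power stated for the RDQ and SF-36 scores rests on a paired t test that the analysis plan does not contain, and no analysis is named as primary

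*Combined protocol and SAP*

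**What the plan says.** **Sample size.** The power for 0.6 RDQ points and 10 SF-36 points with 14 per group is said to hold "when using a paired t test as described in the statistical analyses plan section". Table 3 is a matched-pairs t test calculation, one-tailed, giving a total of 27. The sample size was then recalculated for McNemar: "required sample size was adjusted to a total of 34 patients". A 20% allowance for drop-out gave 42.

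**Primary outcome.** It is defined as a threshold: "Change of ≥ 0,6 points between basal RDQ questionnaire and the same questionnaire administered after 6 weeks of HBE use".

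**Statistic analysis plan.**
- General rule for continuous variables: "For normally distributed continuous variables, statistically significant differences will be searched for by using unpaired Student's t test"; otherwise, "for not normally distributed variables Mann-Whitney U test will be applied". The rule is not limited to baseline data, and the section opens by listing the RDQ and SF-36 among the variables collected.
- McNemar is introduced with "For complementary processing of primary outcome and secondary outcome quality of life, score difference", the difference being that between periods, made binary. The analysis that it complements is not named.
- "Analysis of variance (ANOVA) for crossover studies was used in search for significant sequence, period and treatment effects". No endpoint is attached, and it is not called the main analysis.
- Significance is one-tailed at 0.05.

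**Specific Objectives, item 2** calls for comparing severity and quality of life between the HBE and control groups in the first and in the second period.

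**The concern.** In a 2x2 crossover each patient serves as his or her own control, and the Sample size section takes credit for that. The section to which it refers the reader contains neither a paired t test nor a signed-rank test. The general rule that it does contain, applied to raw scores, would discard the pairing.

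The plan also gives conflicting signals on which p-value decides the trial. One test supplies the power statement for the scores, another sets the sample size, a third is the general rule, a fourth is listed without rank, and the primary outcome is a responder threshold. These tests can give different answers on the same data, so the deciding one could be chosen after results are seen. The power printed for the scores may also not belong to the test that is finally run.

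**Working it through.** **Inputs.** SF-36: difference 10, SD 20.3 ("SF-36 mean and standard deviation of 56,9±20,3 reported in Italian population"), so d = 10/20.3 = 0.4926. RDQ: difference 0.6, SD 1.0, so d = 0.60. One-sided α = 0.05. The documents do not give the within-patient correlation ρ or say that SDs are equal under both conditions. I assume equal SDs and ρ = 0.5, then vary ρ.

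**Step 1: reproduce the plan.** Paired t, n = 27, df = 26: noncentrality 0.4926 × √27 = 2.560, critical t 1.7056, power 0.8016. All match Table 3. With 28 patients the paired test gives 81.5% (SF-36) and 92.6% (RDQ). The arithmetic is sound if 14 per group means 28 patients in all.

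**Step 2: the assumption inside the effect size.** The SD of a within-patient difference is SD × √(2(1−ρ)). It equals the single-score SD only when 2(1−ρ) = 1, that is, ρ = 0.5. Table 3 uses 10/20.3 directly as dz, so it assumes ρ = 0.5 without saying so.

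**Step 3: power under each reading of the unpaired rule, ρ = 0.5.**

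*(a) Period differences compared between sequences.* With N/2 patients per sequence, the noncentrality is dz√N with N−2 df. This is also the one-sided treatment contrast of the crossover ANOVA. At 28: 0.4926 × √28 = 2.607 and 0.60 × √28 = 3.175, critical t 1.7056.

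*(b) Raw scores pooled over periods, pairing ignored.* The test uses SD × √(2/N) as standard error, but the true one is smaller by √(1−ρ) = 0.707. The test is therefore conservative. Normal approximation at 28 for SF-36: (0.4926 × √14 − 1.674)/0.707 = 0.24, about 59%. Simulation gives about 60%, with type I error about 1.1% against a nominal 5%.

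*(c) HBE against control within one period, n per arm.* Noncentrality d√(n/2). With 14 v 14: 1.303 and 1.587.

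| Reading | 28 patients, SF-36 / RDQ | 34 patients, SF-36 / RDQ |
|---|---|---|
| (a) period differences | 81% / 93% | 88% / 96% |
| (b) pooled raw scores | about 60% / 79% | about 69% / 87% |
| (c) single period | 35% / 46% | 41% / 53% |

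**Step 4: vary ρ for reading (a).** At ρ = 0.2, dz is divided by √1.6 = 1.265, giving 0.389 and 0.474. Power at 28 is 64% / 79%; at 34 it is 72% / 86%. To reach 80% at 34 patients, ρ must be at least 0.36 for SF-36 and 0.05 for RDQ.

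**Step 5: ANOVA F test.** The ordinary treatment F test has no direction. At 34 and ρ = 0.5, noncentrality 34 × 0.4926² = 8.25 with 1 and 32 df gives 79.5% for SF-36; 34 × 0.36 = 12.24 gives 92.4% for RDQ. This is below reading (a), because the plan's rule is one-tailed.

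**Step 6: does 42 stand?** With Table 3's McNemar inputs (discordant proportion 0.53782, odds ratio 3.571), 18 discordant pairs and a critical count of 13 give 0.8169, as printed. The mid-p version in the analysis plan gives 81% at 34. Then 34 × 1.2 = 40.8, or 42 in two equal groups. None of this uses the paired t test.

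**The case against.** The strongest reply is that a valid reading is available in the text. McNemar is applied to a dichotomised difference between periods, and calling it complementary suggests a main analysis of that same difference. An unpaired t or Mann-Whitney test of period differences between the two sequences is a correct crossover test, and at ρ = 0.5 it keeps the claimed power. The crossover ANOVA, too, is a within-patient method already in the plan. This stands as far as it goes: a reader might infer that the plan has no valid within-patient test, and that would be wrong. But the period difference is mentioned only in the McNemar sentence, and Specific Objective 2 can be read towards separate comparisons in each period. The text does not settle which is meant.

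Second, most of the shortfall falls on SF-36, a secondary outcome. This is largely right at 34 patients, where RDQ stays above 80% under readings (a) and (b) at ρ = 0.5. At the 28 patients to which the claim is attached, RDQ under (b) is about 79%.

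Third, the analyst works with masked group codes. That limits results-driven choice but does not prevent choosing among p-values.

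Fourth, Table 3 has no separate effect size for RDQ. That is not an error: sizing on the smaller ratio (0.49 against 0.60) covers both scores.

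**Conclusion.** The concern holds in a limited form. The cross-reference is broken, the analysis plan names no main test for the continuous scores, and no analysis is identified as primary. At 28 patients and ρ = 0.5, SF-36 power runs from 35% to 81% and RDQ power from 46% to 93%, depending on how the plan is read. The claim of more than 80% survives under period differences between sequences and fails for both scores under the other two readings. Even where it survives, it depends on an unstated correlation of about 0.5.

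Two stronger conclusions are not supported. A reader might infer that the trial is too small; but 42 comes from McNemar, whose calculation reproduces. A reader might also infer that ignoring the pairing inflates false positives; under positive correlation the pooled test is conservative (about 1.1% at ρ = 0.5), so the cost is power.

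The correlations and equal SDs are assumptions. The absence of the paired test and of a ranking is read directly from the text.

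**What to change.** - Name one within-patient test as the main analysis of the RDQ and SF-36 scores: either the one-sided treatment contrast (signed t) from the crossover ANOVA, or a t or rank-sum test on period differences between sequences. Do not rely on the non-directional F test, which does not match the one-tailed rule.
- Limit unpaired tests on raw values to baseline comparisons.
- State which analysis is primary among this test, McNemar and the 0.6-point threshold in the outcome definition, and label the others supportive.
- Correct the cross-reference in Sample size to the named test, and restate power for each score with the assumed correlation or the SD of within-patient differences.
- Parts of the analysis plan, including the ANOVA sentence, are in the past tense. If any data have already been analysed, label the choice as made after the fact.

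The cost is wording in three sections. No patients or data are added, and 42 does not change. The power for the scores becomes explicitly conditional on the correlation, and if analysis has begun, the choice can no longer count as prespecified.

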Hamilton J, 1988 [Esophagitis]	3	3 days	15	No acid exposure time reduction nor clinical improvement	Low power Short follow-up	19
Pollmann H, 1996 [GERD]	NA	2 weeks	NA	No clinical improvement	Full text unavailable Non-structured abstract	21
Khan BA, 2012 [Nocturnal GERD]	1	1 week	20	↓ acid exposure time, clinical improvement	Non-randomized Inpatient setting	18

Table 1: Summary of HBE clinical trials in GERD published to date. NA: Unavailable; PPI: proton pump inhibitor; ↓: reduction

HYPOTHESIS

Head of bed elevation is a useful treatment for patients with GERD and nocturnal symptoms, and has a positive impact in quality of life in these patients.

STUDY OBJECTIVES

General Objective: To assess the effectiveness of HBE for treatment of patients with GERD and nocturnal symptoms, and to determine the impact of this intervention in quality of life of these patients.

Specific Objectives:

- 1. To identify, recruit and randomize participants with strict allocation concealment.
- 2. To compare symptom severity and quality of life among participants allocated to the HBE and the control group, in both the first and second period of study.
- 3. To assess therapeutic adherence and adverse event occurrence periodically by means of telephone call and photographic documentation of patient compliance with assigned intervention.

PATIENTS AND METHODS

General design: Randomized single-blind single-centre controlled clinical trial with a 2x2 cross-over design, in a sample of patients attending to the outpatient visit at the Gastroenterology, Digestive endoscopy and Liver Diseases Unit in Clínica Fundadores, Bogotá city. Participants who meet the inclusion and have no exclusion criteria will be randomized to raise the head of bed with standard 20 cm-height wooden blocks or to sleep without bed inclination during 2 periods of 6 weeks each, separated by a washout 2 week period. During the trial, every patient will receive standard pharmacological treatment with a proton pump inhibitor and/or sodium alginate, according to treating physician criteria, and the researchers in charge of statistical analysis and reporting results will be blinded for the non pharmacological intervention under study. Primary outcome is a significant symptom reduction according to RDQ validated questionnaire and secondary outcomes include quality of life impact according to SF-36 validated questionnaire, patient preference and adverse events of non pharmacological intervention.

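### Per-period comparisons of RDQ and SF-36 between HBE and control have no adjustment for the week-0 score; ANCOVA would add about 10 points of per-period power at an assumed correlation of 0.5

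*Combined protocol and SAP*

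**What the plan says.** Specific objective 2 (Study Objectives) compares symptom severity and quality of life among "participants allocated to the HBE and the control group, in both the first and second period of study". Within any one period each patient is in one group only, so this is naturally read as a between-patient comparison.

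Under Cross-over and Follow-up, RDQ and SF-36 are repeated at the end of period 1, after washout and at week 14. The outcome definitions and Table 2 also require a basal administration. The primary outcome uses that basal score by subtraction: "Change of ≥ 0,6 points between basal RDQ questionnaire and the same questionnaire administered after 6 weeks of HBE use".

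For continuous variables, the Statistic analysis plan says: "For normally distributed continuous variables, statistically significant differences will be searched for by using unpaired Student's t test". Mann-Whitney is the alternative when normality fails. The plan does not say whether the tested variable is the end-of-period score, the change from basal, or the difference between periods.

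Two analyses compare patients with themselves. One is a McNemar test on the dichotomised between-period score difference. The other is a cross-over model: "Analysis of variance (ANOVA) for crossover studies was used in search for significant sequence, period and treatment effects". Neither names a baseline covariate. The significance rule is "Differences with one-tail p<0,05 will be accepted as statistically significant".

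**The concern.** The week-0 RDQ and SF-36 scores are collected before allocation takes effect and are likely to predict later scores. An unpaired test on end-of-period scores ignores that information. A test on change scores uses it, but with a fixed coefficient of one, which is less efficient than estimating the coefficient. With about 21 patients per group and no stratification in the Randomization section, nothing else in a per-period comparison absorbs baseline variation.

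At stake is the precision of the per-period contrasts that objective 2 asks for. The first-period contrast also has some value of its own because it cannot contain carry-over.

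**Working it through.** **Inputs from the documents.** The Sample size section gives the RDQ target, "minimally important difference as large as or larger than 0,6 points in RDQ questionnaire (range: 1 to 6"), and the RDQ spread, "RDQ mean and standard deviation of 3,3±1,0 previously found in Spanish population". It also gives an SF-36 difference of 10 with SD 20.3, and 42 patients in all, 21 per group. Before the drop-out allowance, "maintaining a statistical power of 80%, required sample size was adjusted to a total of 34 patients", which is 17 per group. Alpha is one-sided 0.05.

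**Input assumed.** The correlation ρ between the week-0 and end-of-period scores is not in the documents. I take 0.5 and show 0.3 to 0.7, with equal SDs at both times.

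**The plan's own figure.** With dz = 10/20.3 = 0.4926 and N = 27, the noncentrality is 0.4926 × √27 = 2.56, and one-sided paired-t power is 0.8016. This matches Table 3. It is a within-patient calculation, so it says nothing about the power of a per-period comparison.

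**Formulas (noncentral t, n per group, difference d).**
- End score, unpaired t: SE = SD·√(2/n), df = 2n − 2.
- Change score, unpaired t: SE = SD·√(2(1 − ρ))·√(2/n), df = 2n − 2.
- ANCOVA: SE = SD·√(1 − ρ²)·√(1 + 1/(2n − 4))·√(2/n), df = 2n − 3.

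**RDQ, n = 21, ρ = 0.5.**
- End score: SE = √(2/21) = 0.309; noncentrality 0.6/0.309 = 1.94; power 60.5%.
- Change score: √(2 × 0.5) = 1, so SE and power are the same, 60.5%.
- ANCOVA: SE = 0.866 × 1.013 × 0.309 = 0.271; noncentrality 0.6/0.271 = 2.22; power 70.3%.

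The gain is 9.8 points on either reading. At 17 per group, RDQ power goes from 52.7% to 61.7%. For SF-36 at 21 per group it goes from 47.0% to 55.7%.

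**Dependence on ρ (RDQ, n = 21; end-score power is 60.5% throughout).**

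| ρ | ANCOVA power | Gain over end score | Gain over change score |
|---|---|---|---|
| 0.3 | 63.0% | 2.5 | 14.2 |
| 0.4 | 66.0% | 5.5 | 12.0 |
| 0.5 | 70.3% | 9.8 | 9.8 |
| 0.6 | 76.2% | 15.7 | 7.3 |
| 0.7 | 84.0% | 23.5 | 4.6 |

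At ρ = 0 the lost degree of freedom costs about 1 point (60.5% to 59.5%).

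**Chance imbalance.** The SD of the difference in basal RDQ means is 1.0 × √(2/21) = 0.31 points. Only the fraction ρ carries into an end-score comparison: 0.5 × 0.31 = 0.15.

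**Reach.** For the within-patient contrast on end-of-period scores, with 34 patients and an assumed between-period correlation of 0.5, RDQ power is already about 96%. Adding start-of-period scores changes it by about 1 point or less. Running that contrast on changes from each period's own start would double its variance and lower power to about 78%.

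**The case against.** The strongest reply is that the per-period test is inferred. The sentence on the unpaired t test is generic and names no questionnaire, period or type of score. In a 2×2 cross-over, an unpaired t test between sequence groups on within-patient period differences is a standard treatment test. The McNemar step, which dichotomises the between-period difference, makes that reading plausible. On it, stable baseline differences cancel and RDQ power at 17 per sequence is about 96%. The text does not exclude this reading. It stands as a limit on the fix: such a test must not be deleted. It does not remove the point, because objective 2 still asks for comparisons in each period, and the plan gives no baseline-adjusted method for them.

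A second reply is that the outcomes are defined as changes, so baseline is already used. That is fair, and it means the word unadjusted fits only the end-score reading. ANCOVA still gains against change scores over the range shown, though by less than 5 points at ρ = 0.7.

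A third reply is that a larger matter lies nearby: the Sample size section relies on a paired t test said to be described in the analysis plan, while that plan names an unpaired one. This is true, but separate. Resolving it would not specify the per-period analysis.

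A reader might go further and infer that the trial's HBE effect as a whole loses about 10 points of power, or is biased by baseline imbalance. The documents do not support either. The cross-over ANOVA and McNemar test are within-patient, and under randomisation chance imbalance is variance that the test's standard error already covers. Nor do the documents make the first period a fallback if carry-over is suspected. They describe a carry-over pre-test and then an ANOVA that assumes carry-over is negligible.

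**Conclusion.** The point holds for per-period HBE versus control comparisons of RDQ and SF-36, and only there. The only test named for such continuous comparisons makes no covariate use of a week-0 score that is already collected. For RDQ at 21 per group the loss is 9.8 points of power if ρ is 0.5. That value is an assumption, and the gain could be as small as 2.5 points (end scores, ρ = 0.3) or as large as 23.5 (end scores, ρ = 0.7). The result also rests on the plan's SDs and on equal SDs at both times. This is a low-cost improvement to a supportive analysis and leaves the validity of the within-patient treatment comparison untouched.

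**What to change.** Add to the Statistic analysis plan that any per-period between-group comparison of RDQ or SF-36 uses a linear model of the end-of-period score on allocated group plus the week-0 score of the same questionnaire. Report the adjusted difference with its interval, and label it supportive of the within-patient cross-over analysis. Use the week-0 score in both periods, because the post-washout score is taken after randomisation and may carry first-period effects.

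Keep the cross-over ANOVA on end-of-period scores (weeks 6 and 14). If an unpaired test between sequences on within-patient period differences is intended, keep it and say so explicitly.

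The cost is a short SAP addition and one regression command in the software already named, with no new data. One degree of freedom is used, about 1 point of power if the correlation is zero.
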